#### *Management Following the Confirmatory Imaging*

If repeat imaging does not confirm PD per iRECIST, as assessed by the Investigator, and the participant continues to be clinically stable, study treatment may continue and follow the regular imaging schedule. If PD is confirmed, participants will be discontinued from study treatment.

NOTE: If a participant has confirmed radiographic progression (iCPD) as defined above, but the participant is achieving a clinically meaningful benefit an exception to continue study treatment may be considered following consultation with the Sponsor. In this case, if study treatment is continued, tumor imaging should continue to be performed following the intervals as outlined in Section 13 and may be submitted to a central imaging vendor during the study per Sponsor’s request.

#### *Detection of Progression at Visits After Pseudo-progression Resolves*

After resolution of pseudo-progression (i.e., achievement of iSD/iPR/iCR), iUPD is indicated by any of the following events:

- Target lesions
  - Sum of diameters reaches the PD threshold ( $\geq 20\%$  and  $\geq 5$  mm increase from nadir) either for the first time, or after resolution of previous pseudo-progression. The nadir is always the smallest sum of diameters seen during the entire trial, either before or after an instance of pseudo-progression.

- Non-target lesions
  - If non-target lesions have never shown unequivocal progression, their doing so for the first time results in iUPD.
  - If non-target lesions have shown previous unequivocal progression, and this progression has not resolved, iUPD results from any significant further growth of non-target lesions, taken as a whole.
- New lesions
  - New lesions appear for the first time
  - Additional new lesions appear
  - Previously identified new target lesions show an increase of  $\geq 5$  mm in the new lesion sum of diameters, from the nadir value of that sum
  - Previously identified non-target lesions show any significant growth

If any of the events above occur, the overall response for that visit is iUPD, and the iUPD evaluation process (see Assessment at the Confirmatory Imaging above) is repeated. Progression must be confirmed before iCPD can occur.

[figure not shown]
The decision process is identical to the iUPD confirmation process for the initial PD, with one exception: if new lesions occurred at a prior instance of iUPD, and at the confirmatory imaging the burden of new lesions has increased from its smallest value (for new target lesions, the sum of diameters is  $\geq 5$  mm increased from its nadir), then iUPD cannot resolve to iSD or iPR. It will remain iUPD until either a decrease in the new lesion burden allows resolution to iSD or iPR, or until a confirmatory factor causes iCPD.

## Imaging and Treatment after First Radiologic Evidence of Progressive Disease

	Clinically Stable		Clinically Unstable	
	Imaging	Treatment	Imaging	Treatment
First radiologic evidence of PD by RECIST 1.1 [For those studies in which PFS is the primary endpoint, add the following: that has been verified by BICR]	Repeat imaging at 4 to 8 weeks to confirm PD.	May continue study treatment at the Investigator's discretion while awaiting confirmatory tumor imaging by site by iRECIST.	Repeat imaging at 4 to 8 weeks to confirm PD per Investigator's discretion only.	Discontinue treatment
Repeat tumor imaging confirms PD (iCPD) by iRECIST per Investigator assessment	No additional imaging required.	Discontinue treatment (exception is possible upon consultation with Sponsor).	No additional imaging required.	Not applicable
Repeat tumor imaging shows iUPD by iRECIST per Investigator assessment	Repeat imaging at 4 to 8 weeks to confirm PD. May occur at next regularly scheduled imaging visit.	Continue study treatment at the Investigator's discretion.	Repeat imaging at 4 to 8 weeks to confirm PD per Investigator's discretion only.	Discontinue treatment
Repeat tumor imaging shows iSD, iPR, or iCR by iRECIST per Investigator assessment.	Continue regularly scheduled imaging assessments.	Continue study treatment at the Investigator's discretion.	Continue regularly scheduled imaging assessments.	May restart study treatment if condition has improved and/or clinically stable per Investigator's discretion. Next tumor imaging should occur according to the regular imaging schedule.

BICR = Blinded Independent Central Review; iCPD = iRECIST confirmed progressive disease; iCR = iRECIST complete response; iRECIST = modified Response Evaluation Criteria in Solid Tumors 1.1 for immune-based therapeutics; iSD = iRECIST stable disease; iUPD = iRECIST unconfirmed progressive disease; PD = progressive disease; RECIST 1.1 = Response Evaluation Criteria in Solid Tumors 1.1.; VOP=verification of progression

**Imaging and Treatment for Clinically Stable Participants Treated with TJ004309 after First Radiologic Evidence of PD Assessed by the Investigator**

## Comparison of RECIST 1.1 and iRECIST Criteria

	RECIST 1.1	iRECIST
Definitions of measurable and non-measurable disease; numbers and site of target disease	Measurable lesions are $\geq 10$ mm in diameter ( $\geq 15$ mm for nodal lesions); maximum of five lesions (two per organ); all other disease is considered non-target (must be $\geq 10$ mm in short axis for nodal disease)	No change from RECIST 1.1; however, new lesions are assessed as per RECIST 1.1 but are recorded separately on the case report form (but not included in the sum of lesions for target lesions identified at baseline)
Complete response, partial response, or stable disease	Cannot have met criteria for progression before complete response, partial response, or stable disease	Can have had iUPD (one or more instances), but not iCPD, before iCR, iPR, or iSD
Confirmation of complete response or partial response	Only required for non-randomised trials	As per RECIST 1.1
Confirmation of stable disease	Not required	As per RECIST 1.1
New lesions	Result in progression; recorded but not measured	Results in iUPD but iCPD is only assigned on the basis of this category if at next assessment additional new lesions appear or an increase in size of new lesions is seen ( $\geq 5$ mm for sum of new lesion target or any increase in new lesion non-target); the appearance of new lesions when none have previously been recorded, can also confirm iCPD
Independent blinded review and central collection of scans	Recommended in some circumstances —eg, in some trials with progression-based endpoints planned for marketing approval	Collection of scans (but not independent review) recommended for all trials
Confirmation of progression	Not required (unless equivocal)	Required
Consideration of clinical status	Not included in assessment	Clinical stability is considered when deciding whether treatment is continued after iUPD

"i" indicates immune responses assigned using iRECIST. RECIST=Response Evaluation Criteria in Solid Tumours. iUPD=unconfirmed progression. iCPD=confirmed progression. iCR=complete response. iPR=partial response. iSD=stable disease.

1 INTRODUCTION

The purpose of this statistical analysis plan is to describe the procedures and the statistical methods that will be used to analyze the efficacy and safety data in accordance with Protocol TJ004309STM103 Version 3.0 dated 30 September 2021. The analysis results will be presented in an abbreviated clinical study report (CSR).

2 OBJECIVES AND ENDPOINTS

2.1 OBJECTIVES

2.1.1 Primary Objectives

- Part 1: To assess the efficacy of TJ004309 combined with atezolizumab in a cohort of patients with platinum-resistant IO naïve ovarian carcinoma and a separate biomarker enriched cohort of subjects with selected tumor types
- Part 2: To further evaluate and confirm the efficacy in targeted patient population based on the efficacy observed in Part 1

2.1.2 Secondary Objectives

- To evaluate the safety and tolerability of TJ004309 when combined with the standard dose of atezolizumab
- Part 1: To characterize the pharmacokinetic profile of TJ004309 when administered in combination with atezolizumab
- Part 1: To determine the immunogenicity of TJ004309 when administered in combination with atezolizumab

2.1.3 Exploratory Objectives

- To investigate the expression of PD-L1, CD73, and other immune subset markers (CD8, CD68, CD19 and CD163) in tumor biopsies at baseline and on treatment, and their associations with clinical responses
- To examine the CD73 enzymatic activity of tumor biopsies
- To study the whole genome gene expression profiles in tumor biopsies

2.2 ENDPOINTS

2.2.1 Primary Endpoints

- Efficacy within each tumor type: ORR by RECIST v1.1

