2.2.2 Secondary Endpoints

- The safety and tolerability of TJ004309 when combined with the standard dose of atezolizumab

- ORR by iRECIST
- Duration of response (DOR) by RECIST v1.1 and iRECIST
- Disease control rate (DCR) by RECIST v1.1 and iRECIST
- Progression-free-survival (PFS) by RECIST v1.1 and iRECIST
- Overall survival (OS)
- Immunogenicity and pharmacokinetic profiles of the combination treatment

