4 STATISTICAL CONSIDERATIONS

4.1 GENERAL CONSIDERATIONS

The below conventions will be used:

- Continuous variables will be summarized using descriptive statistics namely the sample size (n), mean, standard deviation (SD), median, minimum (min) and maximum (max). Mean and median will be rounded to one more decimal place than the original data (up to 3 decimals). Standard deviation will be rounded to two more decimal places than the original data. Minimum and maximum will have the same decimal place as the original data.
- Categorical variables will be summarized using counts and percentages with 2-sided 95% confidence intervals (CIs) where appropriate. Percentages will be rounded to 1 decimal place.
- As Part 2 of the study was not initiated due to an insufficient number of clinical responses observed in Part 1, summary tables and data listings will only be presented for Part 1. Summary tables will be presented by cohort and overall, and data listings will be presented by cohort and subject.

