6.4 PRIMARY TUMOR DIAGNOSIS

Primary tumor diagnosis will be listed by subject.

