8 EFFICACY ANALYSIS

The efficacy evaluable analysis set will be used for the efficacy summary.

The anti-tumor efficacy of the combination of TJ004309 and atezolizumab will be summarized by best of response (BOR) and objective response rate (ORR) assessed by the Response Evaluation Criteria in Solid Tumors (RECIST 1.1) and immune RECIST (iRECIST) guidelines. All tumor response data (including unscheduled tumor assessments) will be used in the efficacy analysis.

Efficacy endpoints such as duration of response (DOR), progression-free survival (PFS) and overall survival (OS) will not be reported due to the abbreviated nature of the CSR to be produced.

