8.3 PRESENTATION

The efficacy summary will include the following:

- Number and percentage of subjects who died before the first response assessment
- Number and percentage of subjects who had at least one response assessment per RECIST 1.1
- Number and percentage of each response (i.e. CR, PR, SD, PD, NE) as the best overall response per RECIST 1.1
- Observed objective response rate (per RECIST 1.1) and the 95% Clopper-Pearson confidence interval
- Number and percentage of subjects who had at least one response assessment per iRECIST
- Number and percentage of each response (i.e. iCR, iPR, iSD, iUPD, iCPD, NE) as the best overall response per iRECIST
- Observed objective response rate (per iRECIST) and the 95% Clopper-Pearson confidence interval

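### The primary endpoint is response rate within each tumor type, but the SAP plans no such estimate for any of the five types pooled in Cohort 2

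*SAP*

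**What the plan says.** SAP 2.2.1 gives a single primary endpoint, "Efficacy within each tumor type: ORR by RECIST v1.1", in the same words as Protocol 3.2.1.

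The SAP's reporting level is set in section 4.1: "Summary tables will be presented by cohort and overall, and data listings will be presented by cohort and subject". Section 8.3 then lists the efficacy outputs, including "Observed objective response rate (per RECIST 1.1) and the 95% Clopper-Pearson confidence interval", and mentions no tumor-type stratum. Diagnosis appears as a listing only, in section 6.4: "Primary tumor diagnosis will be listed by subject".

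Cohort 2 combines five tumor types with a total of up to 30 subjects (SAP 3.1, Table 1). Neither document sets a quota per type.

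The SAP is open about other reductions:
- Part 2, in section 4.1: "As Part 2 of the study was not initiated due to an insufficient number of clinical responses observed in Part 1".
- Time-to-event and duration endpoints, in section 8: "Efficacy endpoints such as duration of response (DOR), progression-free survival (PFS) and overall survival (OS) will not be reported".
- Pharmacokinetic and pharmacodynamic, immunogenicity and biomarker analyses, in sections 10 to 12.

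ORR within tumor type is not among the stated reductions.

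**The concern.** If the SAP is followed exactly, the stated primary endpoint has no planned estimate for any Cohort 2 tumor type. The analysis moves from tumor type to cohort without saying so, which matters more for the only primary endpoint than for a secondary one.

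The pooled Cohort 2 rate is an average weighted by whatever mix of cancers was enrolled. With no quota, that mix is accidental, and the pooled rate is not the rate for any one type. The design itself treated tumor type as the unit of interest: under SAP 3.1, a response in Cohort 2 could lead to a further cohort in one specific type.

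With Part 2 not initiated, no design decision hangs on this. What is at stake is whether the abbreviated clinical study report delivers the endpoint it names.

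**Working it through.** The documents give no null rate, target rate, alpha or power for Part 1, so there is no planned figure to reproduce. The check is a comparison of the texts, followed by an illustration with assumed counts.

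**Comparison of the texts**

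| Question | Where | Answer |
|---|---|---|
| At what level is the primary endpoint defined? | Protocol 3.2.1, SAP 2.2.1 | Each tumor type |
| At what level is the primary objective worded? | SAP 2.1.1 | Cohort: the ovarian cohort and "a separate biomarker enriched cohort of subjects with selected tumor types" |
| At what level are tables produced? | SAP 4.1 | Cohort, and all subjects |
| Does the efficacy section add a level? | SAP 8.1, 8.3 | No |
| Is diagnosis used for grouping? | SAP 6.4 | No, listed only |
| Is by-type ORR declared as dropped? | SAP 4.1, 8, 10 to 12 | No |

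Cohort 1 is entirely ovarian, so its ORR is a single-type estimate, but only for its own population. It requires a high-grade serous component and platinum-resistant or refractory disease (Protocol 5.1, criterion 4a). Ovarian patients in Cohort 2 may have any high-grade epithelial type and must meet a PD-L1 threshold (criteria 5e and 5f). Cohort 1 therefore does not cover them. The all-subjects column mixes both ovarian groups with the other four types.

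**Illustration**

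The inputs are up to 30 subjects in Cohort 2 and five types (SAP 3.1). Per-type sizes are not given and are assumed here: an even split gives 30/5 = 6, or 15/5 = 3 if only 15 enroll. An uneven split might give one type 10.

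The interval is the SAP's own, Clopper-Pearson at 95%. The lower limit is the 0.025 quantile of Beta(x, n − x + 1), and the upper limit is the 0.975 quantile of Beta(x + 1, n − x). For x = 0 the lower limit is 0 and the upper limit is 1 − 0.025^(1/n).

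| Level | x/n | ORR | 95% CI |
|---|---|---|---|
| Cohort 2, full | 2/30 | 6.7% | 0.8 to 22.1% |
| Cohort 2, half | 2/15 | 13.3% | 1.7 to 40.5% |
| One type, n = 6 | 0/6 | 0% | 0 to 45.9% |
| One type, n = 6 | 1/6 | 16.7% | 0.4 to 64.1% |
| One type, n = 6 | 2/6 | 33.3% | 4.3 to 77.7% |
| One type, n = 3 | 0/3 | 0% | 0 to 70.8% |
| One type, n = 3 | 1/3 | 33.3% | 0.8 to 90.6% |
| One type, n = 10 | 0/10 | 0% | 0 to 30.8% |
| One type, n = 10 | 1/10 | 10.0% | 0.3 to 44.5% |

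Two responders among 30 produce the same cohort line whether both have one cancer (2/6 in that type, 0/6 in the other four) or two different cancers (1/6 in each, 0/6 in the other three). The planned table cannot tell these cases apart.

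**The case against.** The strongest reply is that the SAP follows the protocol's analysis section. Protocol 9.2.4 plans response summaries by cohort or group, as far as the data allow, and never promises a table per tumor type. The primary objective is worded by cohort, and the cohort ORR answers it. On this reading the endpoint line is loosely worded and no analysis has been lost. That the cohort ORR answers the objective stands. But the protocol does not define its groups, the SAP does not take up that option, and the SAP restates the by-type endpoint unchanged.

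A second reply is that five rows of three to ten subjects carry almost no information, in a study with no formal sample-size basis and an abbreviated report. The imprecision is real and could be a reason to omit the estimates. The SAP does not give that reason. Its ORR analysis is already descriptive with exact intervals, and small numbers do not rule out the same for tumor types.

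Third, by-type counts could be rebuilt from listings. That is so if the response listing in Protocol 9.2.4 is produced, since diagnosis is also listed. SAP section 8 names no such listing, and a listing is not an estimate.

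Fourth, the rule for opening a further cohort acts on any response together with other data, so it needs the responder's diagnosis and not a rate. That is right. The rule shows only that tumor type was the unit of interest.

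**Conclusion.** The concern holds. The SAP as written yields no estimate of its primary endpoint for HNSCC, NSCLC, gastric cancer, triple negative breast cancer or the ovarian patients in Cohort 2, and does not say so. This is a gap between endpoint and analysis that should be fixed. It does not undermine the cohort-level ORR, and it affects reporting only, because Part 2 was not initiated.

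The textual finding rests on no assumption. The numerical illustration rests on assumed per-type sizes and responder counts. It shows that the pooled rate can conceal very different by-type patterns and that by-type estimates would be imprecise.

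A lesser point of the same kind concerns a secondary endpoint, "Disease control rate (DCR) by RECIST v1.1 and iRECIST" (SAP 2.2.2). It is neither summarized in SAP 8.3 nor named among the endpoints left out in section 8. The list there is worded as examples, so it may have been meant to be included. If disease control means CR, PR or SD (the documents give no definition), the count can be added up from the best-response table, without a label or an interval.

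**What to change.** In SAP 8.3, add one descriptive table on the efficacy evaluable set. For each tumor type within Cohort 2 (NSCLC, HNSCC, gastric, triple negative breast, ovarian) it should show n, best overall response, and ORR by RECIST 1.1 with the 95% Clopper-Pearson interval. Keep Cohort 2 ovarian patients separate from Cohort 1, and keep the cohort-level ORR as the estimate for the primary objective.

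If the table is not produced, SAP section 8 should state that ORR within tumor type is not reported and why. This is the weaker option, since the endpoint would remain unestimated for these types. Either way, section 8 should name disease control rate as not reported if it stays unsummarized.

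The cost is one table from data already collected, or one sentence. The drawback of the table is its wide intervals, so it should be labeled descriptive, with no formal inference drawn for any type.

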2.2.2 Secondary Endpoints

- The safety and tolerability of TJ004309 when combined with the standard dose of atezolizumab

- ORR by iRECIST
- Duration of response (DOR) by RECIST v1.1 and iRECIST
- Disease control rate (DCR) by RECIST v1.1 and iRECIST
- Progression-free-survival (PFS) by RECIST v1.1 and iRECIST
- Overall survival (OS)
- Immunogenicity and pharmacokinetic profiles of the combination treatment

2.2.3 Exploratory Endpoints

- CD73 enzymatic activity of tumor biopsies at baseline and on-treatment tumor biopsies
- Expression of PD-L1, CD73 and other immune subset markers (CD8, CD68, CD19 and CD163)
- Whole genome gene expression profiles in tumor biopsies at baseline and on-treatment tumor biopsies

3 STUDY DESIGN

3.1 OVERALL STUDY DESIGN

This is a multicenter, open label, Phase 2 study of TJ004309 in combination with atezolizumab in patients with advanced or metastatic solid tumors. This clinical study will be conducted in two parts. Part 1 of the study will include two cohorts: Cohort 1 will include Immuno-Oncology (IO) treatment naïve ovarian cancer patients who have progressed on or after platinum therapy; and Cohort 2 will include patients with head and neck squamous cell carcinoma (HNSCC), non-small cell lung cancer (NSCLC), gastric cancer (GC), triple negative breast cancer (TNBC), or ovarian carcinoma with PD-L1 expression $\geq 1\%$ (Table 1). All subjects will be evaluated for antitumor activity on a regular basis as specified in the protocol and their clinical status classified according to RECIST 1.1 and iRECIST. Treatments may continue until clinically significant disease progression, unacceptable toxicity, or subject/Investigator decision to withdraw. Based on the efficacy observation in Part 1, Part 2 of the study will further evaluate the efficacy in selected targeted patient populations and will be initiated after reaching agreement with the regulatory agency.

TJ004309 will be given in combination with atezolizumab 1200 mg every 3 weeks (Q3W) beginning with Cycle 1 Day 1 (C1D1). Premedication will be given prior to the initial infusion of TJ004309 to mitigate infusion related reactions. Each cycle will be 21 days in duration.

Table 1: Study Drug Dosing Schedule - Part 1

Cohort	TJ004309 Q3W	Atezolizumab Q3W	Subjects
Cohort 1: Platinum resistant or refractory IO naïve ovarian carcinoma (OC)	20 mg/kg	1200 mg flat dose	N=30
Cohort 2: HNSCC, NSCLC, GC, TNBC, OC	20 mg/kg	1200 mg flat dose	N=30

Up to 30 subjects will be enrolled in each cohort. If two or less responses are observed from the first 15 subjects in Cohort 1, the enrolment might be stopped based on rules from a Simon's 2-stage design. If 3 or more responses are observed from the first 15 subjects in Cohort 1 from Part 1, then Part 2 of the study may be initiated earlier. If any response is observed from Cohort 2, an additional cohort with up to 30 subjects may be opened with a specific tumor type after reviewing all other available data at that time.

3.2 END OF STUDY DEFINITION

A patient is considered to have completed the study treatment period if they complete the End-of-Study (EOS) visit and, as required, any further follow-up of ongoing serious adverse events (SAEs) regardless of relationship to study drug and/or non-serious adverse events (AEs) considered to be possibly, probably or definitely related to study drug until either resolution or determined by the Investigator to be chronic or stable.

3.3 SAFETY FOLLOW-UP PERIOD

After the treatment periods, all subjects will enter a safety follow-up period and will be evaluated for safety, tolerability, and tumor response (if applicable) for at least 90 days after the last dose of study drug, or 30 days following cessation of study treatment if the subject initiates new anticancer therapy, whichever is earlier. Subjects will be required to return to the study sites for three (3) safety follow-up visits (approximately 30, 60 and 90 days after the last dose of study drug), except those subjects who withdraw consent for study participation. After treatment discontinuation, in the event of continuing serious adverse events (SAEs), subjects will be followed until resolution or stabilization of the SAEs (regardless of the relationship to the IMP). Any subject who has an ongoing non-serious AE that is possibly related or related to the IMP or study procedures at the 90-day post-treatment Follow-up visit will be followed up, where possible, until resolution or until the unresolved non-serious AE is judged by the Investigator (or designee) to have stabilized. Any subject who has an ongoing non-serious AE that is not related or unlikely related to the IMP or study procedures at the Follow-up visit, can be closed out as ongoing at the Investigator's discretion. If a subject initiates a new anticancer therapy within 30 days after the last dose of study treatment, one (1) Post-Treatment Safety Follow-Up visit should occur approximately 30 days after the last dose of study drug and therefore subsequent follow-up visits will not be required.

